6.3. Exploratory Objectives

The exploratory objective of this study is to assess subject preference among the 3 trial lens frames that correct the refractive error measured by the EyeQue VisionCheck, phoropter, and autorefractor.

6.4. Safety Objective

The safety objective of this study is to evaluate the safety of EyeQue VisionCheck compared with the phoropter and the autorefractor.

17

7. INVESTIGATIONAL PLAN

7.1. Overall Study Design

This is a single-center, open-label, prospective study in healthy volunteers desiring refraction for correction of visual acuity to compare the EyeQue VisionCheck with the phoropter and autorefractor. Prior to enrollment of study subjects, both the phoropter and autorefractor devices will be calibrated following standard practice.

Approximately 200 subjects will be enrolled in this study to achieve a minimum of 100 evaluable subjects. The initial cohort included 39 subjects; therefore, approximately 160 additional subjects will be enrolled in the study. Subjects will be enrolled to obtain a population of approximately 35% in the age range of 30 through 44 years and approximately 65% in the age range of 45 through 65 years. Subjects will be screened for study participation and, if enrolled, will complete the testing procedures at the same visit. Subjects will not undergo any study-specific screening or testing procedures until written informed consent is obtained. A subject will be enrolled in the study after confirming that the subject has met all of the inclusion criteria and none of the exclusion criteria.

Screening procedures

The subject will complete the following assessments and procedures at Screening to confirm eligibility:

- demographics/medical history/concomitant medication review,
- slit-lamp biomicroscopy,
- laser retinal scan or fundoscopy,
- optical coherence tomography (OCT) (retina and anterior chamber),
- tonometry (non contact),
- Ishihara color test,
- cover test,
- retinoscopy,
- phoropter refraction, and
- visual acuity with phoropter correction.

During the OCT and laser retinal scan/fundoscopy, images will be taken of the retina, anterior chamber, and fundus. All eye procedures will be completed without dilation using standard procedures.

Retinoscopy will be used as a basis for further refinement by phoropter refraction. Refraction values (sphere, cylinder, axis) for oculus dexter (OD, right eye) and oculus sinister (OS, left eye) will be recorded for each subject using the phoropter. These values will be used to adjust the lenses in the phoropter while the subject is looking through the device at an Early Treatment Diabetic Retinopathy Study (ETDRS) eye chart to determine BCVA, as subjects are eligible to

Version 3.0 (17 June 2019)

participate in the study only if their vision (oculus uterque [OU]; both eyes) can be corrected to 20/20 (logarithm of the minimum angle of resolution [LogMAR] 0.0).

The Screening procedures will be used to confirm that the subject does not have an exclusionary diagnosis.

Testing procedures

Once eligibility is confirmed, the subject will be enrolled and proceed with study testing procedures. The refraction values (sphere, cylinder, axis) for each subject (OD and OS) will be assessed using 2 additional devices: autorefractor and the EyeQue VisionCheck. Subjects will be assessed with the autorefractor using standard device methodology. The refraction values generated from the EyeQue VisionCheck, the autorefractor, and the phoropter (during screening) will be used to prepare 3 sets of trial lens frames. Pupillary distance, measured using the autorefractor, will be recorded for all subjects and will be used for preparation of trial lens frames.

All subjects will be trained on how to use the EyeQue VisionCheck device prior to initiating testing. In order to obtain refraction values using the EyeQue VisionCheck, the subject will be required to take 1 practice test followed by a minimum of 3 saved tests for each eye using the EyeQue VisionCheck device and mobile app. After completion of a set of tests (1 test for each eye), the subject may elect to save or discard that set of tests. They may choose to discard for any reason which may include not following instruction, pressing the wrong button in error, etc. Each test consists of the subject looking through the EveOue VisionCheck device and using the app controls to fully overlap red and green bars at 9 different angles. After completion of all tests (1 practice test and 3 saved tests with each eve), the refraction values will be displayed on the mobile app. These values will be used for preparation of the trial lens frames. If the EyeQue system determines that the overall test results are unreliable, subjects may have to complete 3 additional tests per eye before the system may be able to provide refraction values. Subjects will not be allowed to complete more than 6 saved tests and 1 practice with each eve. The system evaluates the statistical spread of the test results taken by the subject. If the spread is too large, the results are considered to be unreliable and values will not be provided. Such spread can be due to testing error, improper instruction, etc.

After collection of refraction values from each device (phoropter, autorefractor, and EyeQue VisionCheck), the 3 trial lens frames will be prepared and given to the subject in a masked fashion. Best corrected visual acuity will be assessed using the ETDRS eye chart. For each subject, BCVA LogMAR scores will be collected for OD, OS, and OU) for each of the 3 trial lens frames. Subjects will also be asked a question regarding overall satisfaction with visual acuity using each of the 3 trial lens frames. Subjects will be monitored for adverse events (AEs) and adverse device effects (ADEs) during the study.

Appendix 1 presents the schedule of assessments for the study. Section 11 details the study evaluations for screening and testing at the 1 study visit.

7.2. Number of Subjects

Approximately 200 subjects will be enrolled in this study to achieve a minimum of 100 evaluable subjects. The initial cohort included 39 subjects; therefore, approximately

160 additional subjects will be enrolled in the study. Subjects will be enrolled to obtain a population of approximately 35% in the age range of 30 through 44 years and approximately 65% in the age range of 45 through 65 years.

7.3. Study Endpoints

7.3.1. Efficacy Endpoints

Primary Endpoint:

• Statistical non-inferiority of EyeQue VisionCheck compared with phoropter assessed by BCVA (OD, OS, and OU) measured using trial lens frames that correct the refractive error measured by each device analyzed with age stratum 45 through 65 years.

Secondary Endpoints:

- Comparison of raw refraction values produced using the EyeQue VisionCheck and the phoropter analyzed with age strata 30 through 65 years and 45 through 65 years.
- Statistical non-inferiority of EyeQue VisionCheck compared with autorefractor assessed by BCVA (OD, OS, and OU) measured using trial lens frames that correct the refractive error measured by each device, analyzed with age strata 30 through 65 years and 45 through 65 years.
- Comparison of raw refraction values produced using the EyeQue VisionCheck and the autorefractor analyzed with age strata 30 through 65 and 45 through 65 years.
- Statistical non-inferiority of EyeQue VisionCheck compared with phoropter assessed by BCVA (OD, OS, and OU) measured using trial lens frames that correct the refractive error measured by each device analyzed with the age stratum 30 through 65 years.

Exploratory Endpoint:

• Subject preference of trial lens frames that correct the refractive error measured by each of the 3 devices: EyeQue VisionCheck, phoropter, and autorefractor

7.3.2. Safety Endpoints

If any adverse events occur during the study, the safety endpoints will include the frequency and severity of AEs, ADEs, and serious adverse events (SAEs).

7.4. Rationale for Study Design and Control Group

A clinical study based on statistical non-inferiority is the most appropriate means to assess the effectiveness and performance of the EyeQue VisionCheck device relative to the comparator devices, the phoropter and autorefractor, that are standard eye care diagnostic devices used to obtain refraction values.

Masking of the subjects and assessors to the refraction values used to prepare the 3 trial lens frames is appropriate to control and minimize bias in the assessment of BCVA as these LogMAR

scores will be used for determination of statistical non-inferiority. A statistical non-inferiority margin of 0.1 LogMAR has been chosen because the one-line ETDRS difference is an acceptable boundary for corrected visual acuity, with larger differences likely to be unacceptable to patients and smaller differences difficult to reliably detect and/or reproduce.

Based on the intended use for obtaining refraction values, a one-day evaluation is appropriate because standard-of-care eye exams in which refraction values are obtained are typically repeated on a periodic basis, such as yearly, and it is not anticipated that refraction values would change over a short duration where additional repeated measurements would be necessary for this study. Visual acuity may fluctuate often; however, there is no appreciable change over a period of a several months.

The design allows for enrollment of subjects 30 to 65 years because subjects younger than 30 years of age are more likely to have visual accommodation that would add complexity to this comparative study. Younger subjects may be assessed in a separate clinical study.

8. SELECTION AND WITHDRAWAL OF SUBJECTS

8.1. Subject Inclusion Criteria

Subjects must meet all of the following inclusion criteria to be enrolled in the clinical study:

- 1. Male or female
- 2. Age 30 through 65 years at time of consent
- 3. Binocular vision
- 4. Subject desires refraction for correction of visual acuity and vision (OU) can be corrected to 20/20 (LogMAR 0.0)
- 5. Willing and able to give informed consent and follow all study procedures and requirements
- 6. Ability to speak and understand the English language

8.2. Subject Exclusion Criteria

The presence of any of the following exclusion criteria excludes a subject from study enrollment:

- 1. Spherical correction > +8 or < -10
- 2. Using anticholinergic medications (including first-generation antihistamines) or other medications known to affect visual acuity within the greater of 3 days or 5 half-lives prior to enrolling in this study
- 3. Using an investigational drug or approved therapy for investigational use within the greater of 3 days or 5 half-lives prior to enrolling in this study
- 4. Has initiated any new medication in the past 2 weeks that, in the best medical judgment of the investigator, would impact their participation in the study or ability to use the EyeQue VisionCheck device
- 5. Eye disease, including but not limited to:
 - Glaucoma (\geq 22 mmHg intraocular pressure)
 - Cataracts (≥ 1+ nuclear sclerotic cataract, ≥ 1+ cortical, posterior subcapsular cataract [any grade using the Lens Opacities Classification System III])
 - Macular degeneration (retinal pigmented epithelium mottling and/or any drusen within 500 µm of macula)
 - Eye infection (corneal ulcer, corneal infiltrates, superficial punctate keratitis)
 - Keratoconus
 - Diabetic neuropathy/retinopathy (> mild nonproliferative diabetic retinopathy)
 - Cytomegalovirus retinitis
 - Color blindness (any color deficiency)

Version 3.0 (17 June 2019)

- Diabetic macular edema (evidence of fluid)
- Amblyopia
- Chronic or acute uveitis (cells and/or flare in anterior chamber)
- Strabismus (exotropia, esotropia, and hypertropia)
- Abnormal astigmatism (mild to severe, > 5 diopters)
- Macular hole
- 6. Eye surgery within the last 12 months (including Lasik or lens replacement)
- 7. Subject does not have the physical dexterity to properly operate the EyeQue VisionCheck device or the EyeQue app on the smartphone in the investigator's opinion

8.3. Subject Withdrawal Criteria

Subjects may be withdrawn from treatment or assessment for the occurrence of an adverse effect or any other conditions that may create a safety risk. Subjects may also be withdrawn at the discretion of the investigator.

Subjects can withdraw consent at any time for any reason without effect on subsequent care. Any enrolled subjects desiring to discontinue prior to study completion should be encouraged to discuss his or her reasons and concerns with the investigator. A subject who discontinues during the study visit prior to completion of all study procedures may be replaced.

8.4. Study Termination

If the study is suspended or prematurely terminated, the appropriate institutional review board (IRB)/independent ethics committee (IEC) and regulatory authority(ies) will be promptly informed of the termination/suspension and will be provided the reason(s) for the termination/suspension. All obligations and responsibilities of the sponsor and the investigator under the United States (US) Code of Federal Regulations (CFR) will remain in force if the study is terminated prematurely.

This study may be discontinued at any time if, in the opinion of the investigator, in consultation with the medical monitor and EyeQue, continuation of the study represents a significant medical risk to participating subjects. All unanticipated ADEs, will be examined to determine whether the ADE presents an unreasonable risk to subjects. If deemed an unreasonable risk, the study will be terminated or suspended.

9. TEST ARTICLE

9.1. Description

The investigational device is the EyeQue VisionCheck, and the intended use is to measure the refractive error of the eye. The EyeQue VisionCheck is a self-administered, portable, monocular refraction system consisting of 3 main components: a mobile app, a cloud-based processing platform, and the VisionCheck optical device that attaches to a compatible smartphone owned/operated by the end user. The EyeQue app guides the subject through interactive measurements with the EyeQue VisionCheck device in order to determine refractive error. The device and mobile app operate on the inverse Shack-Hartmann principle described in patent US 8783871 B2, "Near Eye Tool for Refraction Assessment" (Pamplona V, US Patent, 2014).

The EyeQue VisionCheck device is manufactured for EyeQue Corporation.

9.2. Packaging, Labeling, and Dispensing

All material containers will be appropriately labeled with the study number and product identification as applicable, as well as any other information as required by applicable regulations.

The compatible smartphones and access to the app will be provided to the sites to be used with the EyeQue VisionCheck.

9.3. Storage and Accountability

All test articles will be stored in a secure location at the investigational site.

A log of all test articles received and used during the study will be maintained by the study site. All test articles will be accounted for at the termination of the study and a written explanation provided for any discrepancies. The EyeQue VisionCheck devices and smartphones will be returned to EyeQue. Shipping and handling of all test articles will conform to regulations for investigational devices.

9.4. Device Risk Analysis and Risk Assessment

The device risk analysis and risk assessment were conducted in compliance with 21 CFR 820. Based on this assessment, the EyeQue VisionCheck is non-invasive and considered a low-risk device that requires periorbital surface contact. Even if the EyeQue VisionCheck is misused, the likelihood it will cause harm is low. The comparators in this study, phoropter and autorefractor, are used as part of standard eye exams. Most of the anticipated adverse effects are generally well tolerated and would be expected to occur infrequently. The risk and impact of these adverse effects is low.

Based on the design and the intended use of the EyeQue VisionCheck, and given the low risk of potential adverse effects, this is considered a nonsignificant risk medical device study that is subject to abbreviated investigational device exemption (IDE) regulations, and exempt from the requirement to submit an IDE application.

The following adverse effects may potentially occur with the use of the EyeQue VisionCheck device itself, the comparators, or the procedure used for the device:

- Transient blurred vision
- Transient dizziness
- Headache
- Transient eye irritation
- Superficial eye or periorbital infection

The following approaches have been used to minimize risk in this investigation:

- Subjects will be screened before receiving treatment to ensure they meet the protocol-defined inclusion and exclusion criteria. The inclusion and exclusion criteria have been developed to ensure appropriate subjects are included in the studied population and subjects with confounding conditions or conditions that could put them at risk are excluded from participation.
- The test articles (investigational and comparator devices) are intended for measuring refraction values and/or accessing BCVA. To minimize risk during the evaluations, the site staff will be trained on all devices and subjects will be instructed how to use each device. The phoropter and autorefractor are both operated by the site staff. The EyeQue VisionCheck device will be operated by the subject and subjects will be trained in advance of completing testing with the device. The mobile app provides detailed instructions on how to operate the EyeQue VisionCheck device. Detailed instructions for the site staff to provide to subjects about the EyeQue VisionCheck are provided in the study operations manual.
- To minimize the risk of eye irritation or infection, the devices will be sanitized between users.
- Adverse device effects will be monitored throughout the study by site staff.

If an adverse event occurs, site staff will follow medical procedures appropriate to the type of event.

10. TREATMENT OF SUBJECTS

10.1. Concomitant Medications

Any treatment including all prescription drugs, herbal products, vitamins, minerals, and over-the-counter medications or therapies administered from the time of consent through the end of study participation is considered a concomitant medication. Concomitant medication use will be recorded in the subject source documentation and may include the medication name, dose, frequency, route of administration, and the dates of administration.

10.1.1. Prohibited Concomitant Medications

The following concomitant medications and therapies are prohibited for the duration of the study and cannot be used within the greater of 3 days or 5 half-lives prior to enrolling in this study, unless otherwise specified:

- Anticholinergic medications (including first-generation antihistamines)
- Medications known to affect visual acuity
- Investigational drugs or approved therapies for investigational use

10.1.2. Permitted Concomitant Medications

Other than the prohibited medications and therapies listed in Section 10.1.1, treatment with concomitant medications and therapies is permitted during the study. Concomitant medication deemed necessary for the welfare of the subject during the study may be given at the discretion of the investigator.

10.2. Treatment Compliance

The investigational device will be used on site with the assistance of a study staff member during the study visit and thus is an observed compliance. The number and percentage of subjects not completing assessments on each device will be reported.

10.3. Randomization and Masking

10.4. Randomization

Not applicable to this clinical study.

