10.5. Masking

This is an open-label study and the site and subjects will not be masked to the assessment device. Three sets of trial lens frames will be prepared using the refraction values from the 3 devices, including the EyeQue VisionCheck, phoropter, and autorefractor. During the study, the subjects and site personnel performing the BCVA assessments will be masked to the refraction values that are used to prepare each of the trial lens frames. Masking regarding the trial lens frames will

be maintained throughout the study by use of separate site personnel to prepare the frames and perform the BCVA assessment.

If the site personnel performing the BCVA assessments or a subject is unmasked, the subject must be discontinued from the study. Additionally, the sponsor and or designee must be notified.

27

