11.2.1.2. Testing procedures

Once eligibility is confirmed, the subject will be enrolled and proceed with study testing procedures.

The following testing procedures and assessments will be completed:

- Refraction values (sphere, cylinder, axis) for OD and OS using the autorefractor
- Measurement of pupillary distance using the autorefractor; pupillary distance will be used for preparation of trial lens frames

• Refraction values (sphere, cylinder, axis) for OD and OS using the EyeQue VisionCheck; all subjects will be trained on how to use the EyeQue VisionCheck device prior to initiating testing

In order to obtain refraction values using the EyeQue VisionCheck, the subject will be required to take 1 practice test followed by a minimum of 3 saved tests for each eye using the EyeQue VisionCheck device and mobile app. After completion of a set of tests (1 test for each eye), the subject may elect to save or discard that set of tests. They may choose to discard for any reason which may include not following instruction, pressing the wrong button in error, etc. Each test consists of the subject looking through the VisionCheck device and using the app controls to fully overlap red and green bars at 9 different angles. After completion of all tests (1 practice test and 3 saved tests with each eye), the refraction values will be displayed on the mobile app. If the EyeQue system determines that the overall test results are unreliable, subjects may have to complete 3 additional tests per eye before the system may be able to provide refraction values. Subjects will not be allowed to complete more than 6 saved tests are unreliable, no values will be provided.

- Best corrected visual acuity (LogMAR scores for OD, OS, and OU) assessed using the ETDRS eyechart and trial lens frames produced from:
 - Phoropter refraction values
 - Autorefractor refraction values
 - EyeQue VisionCheck refraction values
 - *Subject and assessor will be masked to the refraction values used to produce the trial lens frames
- Subject preference regarding each of the trial lens frames
- Adverse event recording

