12.1.1. Best Corrected Visual Acuity

Best corrected visual acuity will be measured using trial lens frames prepared based on the refractive error measured by each device including the EyeQue VisionCheck, phoropter, and autorefractor. Best corrected visual acuity will be assessed using the ETDRS eye chart. For each subject, BCVA logMAR scores will be collected for OD, OS, and OU for each of the 3 trial lens frames.

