13. STATISTICS

13.1. Power and Sample Size Determination

Approximately 200 subjects will be enrolled in this study to achieve a minimum of 100 evaluable subjects to assess the effectiveness and safety of the EyeQue VisionCheck. The initial cohort included 39 subjects; therefore, approximately 160 additional subjects will be enrolled in the study. Based on prior study data, rejection of non-inferiority bounds of 0.1 LogMAR (one line) and 0.05 LogMAR (one-half line) would require approximately 10 and 40 subjects, respectively, with 90% power on the BCVA from the resulting lens from each approach. This assumes the devices are roughly equivalent and the standard deviation (SD) is 0.077; these data are based on a previous version of the EyeQue VisionCheck device tested against an autorefractor. The proposed sample size has been inflated to allow for the possibility that a larger standard deviation will be observed in the current study, as well as to allow for comparisons within each stratum. A software error in the EyeOue app was identified and the algorithm for the EyeQue app was updated with more stringent parameters which may also impact the number of evaluable subjects. Due to the updates to the parameters, there may be additional subjects for which EyeQue VisionCheck refraction values are not produced, leading to an increase in the number of subjects that will not be evaluated for the primary endpoint. Of the approximately 160 additional subjects that will be enrolled in the study, it is anticipated that approximately 60 subjects will not be evaluable due to failing screening or not having refraction values produced with the EyeQue VisionCheck. Additionally, the larger sample size provides a sufficiently robust database for investigations of the secondary outcomes and descriptions of the EveQue VisionCheck's performance characteristics.

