13.3. Efficacy Analyses

Best corrected visual acuity will be assessed independently for each eye and the worse value for each test lens set and subject will be selected for the primary analysis. Each subject's BCVA LogMAR score from the phoropter-based lenses will be subtracted from the BCVA LogMAR

Version 3.0 (17 June 2019)

score from the EyeQue VisionCheck-based lenses. The mean, SD, and two-sided 95% confidence interval (CI) will be reported across all subjects for worst eye, OD, OS, and OU, and if the upper bound (one sided 95% CI) does not include the value 0.1 for the worst eye comparison, then non-inferiority will be declared. This will be repeated using BCVA scores from the autorefractor-based lenses and EyeQue VisionCheck-based lenses.

Raw refraction values for the phoropter and VisionCheck will be plotted and Pearson correlations calculated. This will be repeated using autorefractor and EyeQue VisionCheck values.

Subject preference data will be tabulated with counts and percentages of subjects that considered the EyeQue VisionCheck trial lenses better as well as the counts and percentages of subjects that considered the EyeQue VisionCheck trial lenses better or equal.

Analyses will be repeated for each age stratum including ages 30 through 65 and ages 45 through 65.

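### The reading order of the three trial frames is not set, balanced or recorded in the plan, so a consistent order would confound practice or fatigue with device in the primary BCVA comparison

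*Combined protocol and SAP*

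**What the plan says.** - Section 10.4 (Randomization), in full: "Not applicable to this clinical study".
- Section 7.1 (Overall Study Design) says that "the 3 trial lens frames will be prepared and given to the subject in a masked fashion". It gives no order.
- Section 7.4 says that masking "is appropriate to control and minimize bias in the assessment of BCVA". Section 10.5 says what is masked: "subjects and site personnel performing the BCVA assessments will be masked to the refraction values". It adds that different staff prepare the frames and test acuity.
- Section 11.2.1.2 calls for "Best corrected visual acuity (LogMAR scores for OD, OS, and OU) assessed using the ETDRS eyechart and trial lens frames produced from" a list running phoropter, autorefractor, VisionCheck. Section 12.1.1 refers to the "refractive error measured by each device including the EyeQue VisionCheck, phoropter, and autorefractor", so VisionCheck comes first there, as it does in section 10.5. None of these lists is described as a running order.
- Section 12.1.1 collects LogMAR scores for OD, OS and OU with each frame. It names no order or period variable.
- Section 13.3 defines the primary contrast: "Each subject's BCVA LogMAR score from the phoropter-based lenses will be subtracted from the BCVA LogMAR" score from the VisionCheck-based lenses. Non-inferiority is declared if the one-sided 95% upper bound for the worst eye excludes 0.1. The analysis has no order term.

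**The concern.** Because every subject uses all three devices, there is no allocation of subjects to devices to randomise. The order of reading is a separate matter. The three frames give nine acuity readings in one sitting (3 frames × OD, OS, OU), after three more at screening. Acuity scores can improve with practice on the chart or worsen with fatigue. A frame can be fully masked and still always be read last, so masking does not separate device from position.

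If the site happens to follow one order, any position effect becomes part of the VisionCheck minus phoropter difference that decides the primary question. It can act in either direction: practice favours the frame read later, fatigue the frame read earlier. If the order varies but is not recorded, nobody can check afterwards whether it mattered. The autorefractor comparison (section 13.3) and the preference ranking (section 12.1.3) have the same gap.

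**Working it through.** **Inputs from the documents**
- Margin 0.1 LogMAR (section 7.4); decision at one-sided 5% (section 13.3).
- At least 100 evaluable subjects, about 65% of them aged 45 through 65 (sections 7.2 and 13.1). Hence n = 0.65 × 100 = 65 in the primary stratum, assuming the enrolment share carries over to evaluable subjects.
- SD and true difference (section 13.1): "This assumes the devices are roughly equivalent and the standard deviation (SD) is 0.077".

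**Inputs assumed**
- A consistent order, and a total bias *b* in the VisionCheck minus phoropter mean. The documents give no value for *b*.

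**Which SD**

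Section 13.1 states about 10 and 40 subjects for margins of 0.1 and 0.05 at 90% power. With z₀.₉₅ + z₀.₉₀ = 2.926:
- 2 × (0.077 × 2.926 / margin)² gives 10.2 and 40.6, which matches the plan.
- (0.077 × 2.926 / margin)² gives 5.1 and 20.3, which does not.

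The plan's numbers therefore correspond to an SD of the difference of 0.077 × √2 = 0.109. The text does not say whether 0.077 is already the SD of the difference, so both values are carried below.

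**Effect of a constant bias**

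P(declare non-inferiority) = P(T > 1.669), where T is noncentral t with 64 df and noncentrality (0.1 − (true difference + b)) / (SD/√65).

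The standard error SD/√65 is 0.00955 (SD 0.077) or 0.01352 (SD 0.109). For a true difference of 0.1 and b = −0.02, the noncentrality is 0.02/0.00955 = 2.09 or 0.02/0.01352 = 1.48.

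| True difference | Bias b | SD 0.077 | SD 0.109 |
|---|---|---|---|
| 0.1 (at margin) | 0 | 5% | 5% |
| 0.1 | −0.01 | 27% | 18% |
| 0.1 | −0.02 | 67% | 43% |
| 0.05 | 0 | >99% | 98% |
| 0.05 | +0.02 | 93% | 71% |
| 0 | +0.05 | >99% | 98% |

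The first three rows are false non-inferiority; the last three are power. Negative b favours VisionCheck. The bias does not shrink as n grows. At n = 100 and SD 0.077, the 67% becomes 83%.

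**Effect of balancing the order**

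Over the six possible orders, the position of VisionCheck minus the position of phoropter takes the values −2, −1, −1, 1, 1, 2. The mean is 0 and the variance is (4+1+1+1+1+4)/6 = 2. A shift of 0.02 per position then gives:
- mean bias 0;
- added variance 2 × 0.02² = 0.0008;
- SD √(0.077² + 0.0008) = 0.082, or √(0.109² + 0.0008) = 0.113;
- false non-inferiority 3.9% / 4.5% (simulated, 40,000 runs, n = 65);
- power at a true difference of 0.05: >99% / about 97%.

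The two settings match when VisionCheck and phoropter are read in adjacent positions, because a shift of 0.02 per position is then a total bias of 0.02. Two positions apart, a fixed order would give a bias of 0.04, and false non-inferiority at the margin would be 99% / 90%.

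**The case against.** The strongest reply is that nothing shows a fixed order or a position effect. Four parts of it deserve weight.

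- *Unseen documents.* The eCRF is not included, and the study operations manual cited in section 9.4 is not available. Either could hold an order rule or an order field. This stands as a limit: the claim concerns what the protocol and SAP state. Section 9.4 cites the manual for instructions to subjects on VisionCheck. If a rule exists elsewhere, it still belongs in the protocol.
- *Masking.* A fixed order known to the assessor would reveal the device and sit badly with section 10.5. That makes a consistent order less likely. It does not exclude one, and it neither balances nor records the order.
- *Screening reading.* Every subject has already read the chart for OD, OS and OU with phoropter correction (section 11.2.1.1), so some practice gain may be used up. That may reduce a practice effect but does not touch fatigue.
- *Stacked assumptions.* The 67% / 43% needs a consistent order, a bias of 0.02 in the favourable direction and a true deficit at the margin. With the same bias, false non-inferiority is back to 5% at a true deficit of 0.12 and below 1% at 0.13. Under true equivalence, an adverse bias must exceed about 0.07 (SD 0.077) or 0.06 (SD 0.109) before power falls below 90%. All of this is correct, and it limits how often the problem would change the result.

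It is also fair that section 10.4 is right about allocation to devices. The fault is what it leaves out.

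**Conclusion.** The concern holds in its conditional form. The plan does not specify, balance or provide for recording the frame order, and neither masking nor the primary analysis compensates for that. Under a consistent order, even a bias of 0.01 to 0.02 LogMAR, one-tenth to one-fifth of the margin, would raise false non-inferiority at the margin from 5% to between 18% and 67%, depending on the bias and the SD. These figures rest on an assumed order, an assumed bias and n = 65. The documents fix neither the sign nor the size of the effect.

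If the devices are equivalent, the pass/fail result is safe. The exposure is to a true difference part-way to or at the margin, where a non-inferiority test has to be reliable. This should be fixed because the remedy is cheap and an unrecorded order cannot be recovered later.

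**What to change.** Replace the entry in section 10.4 with text such as:

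> Subjects are not randomised to devices. The order in which the three trial frames are read is assigned from a pre-generated list that balances the six possible orders in blocks of six within age group (30–44, 45–65). The order is assigned only after all three sets of refraction values exist. The staff who prepare the frames hold the list and label the frames A, B and C by reading position, so that a label does not identify a device. The order is recorded in the eCRF.

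Keep the primary analysis in section 13.3. Add a supportive mixed model of worst-eye BCVA with device and position as fixed effects and subject as a random effect, reporting the VisionCheck minus phoropter estimate and its one-sided 95% upper bound.

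The cost is one list, one eCRF field, one supportive analysis and an amendment. Section 10.5 already separates preparers from assessors, so no extra staff, subjects or visits are needed. There are two downsides: a small rise in variance if position is left unmodelled, and no balance among subjects tested before the amendment.
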